3. OBJECTIVES AND ENDPOINTS

The objectives and corresponding endpoints provided in Table 4, apply to:

- Part A: RO7121661 single agent dose escalation phase
- Part B: RO7121661 single agent expansion in selected indications

Table 4 Objectives and Endpoints

Objectives	Endpoints
Primary	
Dose Escalation: Safety, tolerability, MTD and/or RDE.	 Nature and frequency of DLTs and other AEs, PD and PK profile.
	 Incidence, nature and severity of AEs graded according to the National Cancer Institute (NCI) Common Terminology Criteria for Adverse Events (CTCAE) v5.0.
Expansion: Assessment of the anti-tumor activity of RO7121661.	 According to Response Evaluation Criteria in Solid Tumors (RECIST) Version 1.1 criteria:
	 Objective response rate (ORR).
	 Disease control rate (DCR); defined as ORR+stable disease rate (SDR).
	 Duration of response (DoR).
	 Progression free survival (PFS) defined as the time from the first study treatment (Day 1) to the first occurrence of progression per Investigator assessment or death from any cause, whichever occurs first.
Secondary	
To characterize the immunogenicity profile of RO7121661 (Part A and B).	Incidence of anti-drug antibodies (ADAs).
To explore potential PD-1, TIM-3 and PD-1/TIM-3 specific PD biomarkers (Part B).	 Examine the profile and status of T cell proliferation/activation in tumor biopsies and peripheral blood.
To investigate the single and multiple dose PK of RO7121661 (Part A and B).	 PK profiles and parameters derived for RO7121661.
To explore degree of target binding of RO7121661 (in association with PK/PD) via RO (Part A).	Evaluate RO via ex-vivo assay.
To evaluate the safety and tolerability of RO7121661 (Part B).	 Incidence, nature and severity of AEs graded according to the NCI CTCAE v5.0.
To explore preliminary anti-tumor activity of RO7121661 (Part A).	 According to RECIST Version 1.1 criteria: Objective response rate (ORR).
	 Disease control rate (DCR).
	 Progression-free survival (PFS).
	 Duration of response (DoR).

Table 4 Objectives and Endpoints (cont.)

Objectives	Endpoints
Tertiary/Exploratory	
To make a preliminary assessment of the anti-tumor activity of RO7121661 using immune-related RECIST (iRECIST) (Part A and B).	 Investigator-determined assessment using iRECIST:
	o ORR.
	 DCR; defined as response rate (RR)+stable disease (SD).
	o DoR.
	 PFS defined as the time from the first study treatment (Day 1) to the first occurrence of progression per Investigator assessment or death from any cause, whichever occurs first.
 To make a preliminary assessment of overall survival from RO7121661 (Part A and B). 	 Overall survival (OS), defined as the time from first study treatment to death from any cause (if data mature at the time of analysis).
To explore and identify potential PD biomarkers in association with exposure kinetics (Part A and B).	 Examine PD changes in the following compartments:
	 Tumor Microenvironment (pre– and on-treatment tumor biopsies): Measure changes in degree and extent of T-cell infiltration and inflammatory gene expression profiles/signatures.
	 Peripheral Blood: Serial sampling to assess kinetic changes in select T-cell subsets, inflammatory cytokines, soluble factors, gene signatures and monitoring tumor burden.
 Correlation of anti-tumor activity of RO7121661 to PK, PD and safety (Part A and B). 	 Compare anti-tumor activity by RECIST with PK parameters, PD changes and safety events.

ADAs = anti-drug antibodies; AEs = adverse events; ctDNA = circulating tumor DNA; DCR = Disease control rate; DLTs = dose-limiting toxicities; DoR = Duration of response; iRECIST = immune-related RECIST; IV = intravenous; MTD = maximum-tolerated dose; NCI CTCAE = National Cancer Institute Common Terminology Criteria for Adverse Events v5.0; ORR = Objective response rate; OS = Overall survival; PD = pharmacodynamics; PFS = Progression free survival; PK = pharmacokinetic; RDE = recommended dose for expansion; RECIST = Response Evaluation Criteria in Solid Tumors; RO = receptor occupancy; RR = response rate; SD = stable disease; SDR = stable disease rate; TMB = tumor mutational burden.

4. STUDY DESIGN

4.1 OVERALL DESIGN

An overview of the study design is provided in Section 1.2.

Study NP40435 is a first-in-human, open-label, multicenter, Phase I multiple-ascending dose (MAD) study of single agent RO7121661. The study consists of 2 parts (A and B):

- Part A (RO7121661 Dose Escalation): To determine the MTD and/or RDE based on safety, tolerability, PK, and/or the PD profile of escalating doses of RO7121661 every 2 weeks (Q2W). If for specific cleared cohort(s) the safety, PK and/or RO and/or the biomarker profile need to be further characterized, additional participants, potentially enriched in certain indications and/or characteristics, may be enrolled.
- Part B (RO7121661 Tumor-Specific Expansion Cohorts): To evaluate anti-tumor activity of the RDE of RO7121661 from Part A (2.1 g Q2W) and to confirm safety and tolerability in participants with selected tumor types. B1, B2, B4 and B5 expansions may be staggered, sequential or concurrent. Part B3 will not proceed prior to generation of data from the initial CPI experienced indication(s):
 - Part B1: CPI experienced second line and beyond metastatic melanoma
 - Part B2: CPI and platinum experienced second or third line PD-L1 positive NSCLC
 - Part B3: PD-L1 positive, CPI naïve, first line NSCLC
 - Part B4: CPI-naïve SCLC with prior failure of, progression on, or intolerance to standard therapy
 - Part B5: CPI-naïve ESCC

Part A of the study will enroll participants with solid tumors who have progressed on a cancer therapy or who are not amenable to standard of care. At least DLT evaluable participants will be enrolled in each cohort during the dose escalation (see Section 4.1.3). Dose escalation will be carried out according to a modified continual reassessment method (mCRM) with escalation with overdose control (EWOC) design, with the aim of identifying the MTD/RDE of RO7121661.

Since RO7121661 will be administered Q2W in Part A, the cycle length will be defined as 14 days. The maximum total number of participants in the dose escalation portions of Part A1 will be approximately DLT evaluable participants on a Q2W schedule. A dose cohort can be extended to enroll additional participants (approximately), potentially enriched in certain tumor types and/or characteristics to confirm safety, PK and/or RO and/or the biomarker profile.

Part B1 and/or B2 and/or B4 and/or B5 may commence upon completion of Part A. The starting dose of RO7121661 for Part B is 2.1 g Q2W as derived from the RDE in Part A

determined by safety, PK and/or RO and/or the biomarker profile. Part B3 will not proceed prior to generation of data from the initial CPI experienced indication(s).

Patients enrolled in Part B expansions have more specific limitations of prior therapies for inclusion than during the dose escalation. Patients enrolled in Part B1 (CPI experienced melanoma) must have had treatment with approved anti-PD-L1/anti-PD-1 checkpoint inhibitors. Patients enrolled in Part B2 (CPI and platinum experienced, PD-L1 expression \geq 1% NSCLC) must have had a checkpoint inhibitor and platinum chemotherapy. Patients enrolled in Part B3 (untreated, CIT naïve NSCLC with PD-L1 expression \geq 50%) should not have had any prior therapy. Patients enrolled in Part B4 (CPI naïve SCLC) and B5 (CPI-naïve ESCC) should not have had any prior checkpoint inhibitor therapy but may have had chemotherapy. Specific details for Part B Expansions are included in the Inclusion and Exclusion Criteria (Section 5.1 and Section 5.2).

In Part B (tumor specific expansion cohorts) approximately participants will be included per indication. Part B cohorts may run in parallel, staggered or sequentially.

Participants will be treated with RO7121661 until disease progression, unacceptable toxicities, or withdrawal of consent. Participants may continue treatment with RO7121661 (Part A and B) for 24 months or longer if the participant is still benefitting from treatment at the time of the last visit at the end of the two-year period. As with other immunotherapies, treatment beyond progressive disease according to RECIST Version 1.1 can be considered after consultation and agreement between the Sponsor and Investigator.

4.1.1 Length of the Study

The duration of the study for each participant will be up to 27 months (Parts A and B), divided as follows:

- Screening: Days 28 to 1
- Treatment Period: Cycle 1 Day 1 to Month 24 (may be modified if supported by emerging data).
- Safety follow-up: 60 (\pm 7) days after last treatment with RO7121661 for Part A; 90 (\pm 7) days after last treatment with RO7121661 for Part B.
- Survival follow-up: 90 (\pm 7) days after last treatment with RO7121661; then every 3 months (\pm 2 weeks) for total 24-month period after initial dose.

The treatment period may be prolonged past month 24 if the participant is still benefitting from treatment at the time of the last visit at the end of the two-year period. Participants may extend treatment within the ongoing study whether they are on treatment or are on a treatment pause at the 24-month time point. During the extended treatment period, the participant follows the SoA as indicated for "Subsequent Cycles." Participants will be treated until disease progression, unacceptable toxicities, or

withdrawal of consent. For participants who extend their treatment, the safety follow-up will be performed 60 (\pm 7) days for Part A or 90 (\pm 7) days for Part B after the last treatment with RO7121661 and survival follow-up every 3 months (\pm 2 weeks) thereafter for a total of 48 months after initial dose, or end of the study.

4.1.2 Dose-Escalation Decision Criteria

For Part A, RO7121661 dose-escalation will be carried out according to a mCRM with EWOC design and will be based on the occurrence of DLTs. The dose-toxicity relationship is described by a 2-parameter logistic regression model, where the probability of DLT is expressed as a function of dose. The model is continuously updated as additional participant information becomes available (for further information see Appendix 10).

A minimum of participants per cohort will be enrolled and treated in a sequential manner with one week between the first and second participant and at least 2 days between subsequent participants. However, if the first participant experiences a DLT within the first week, then the time between the treatment of subsequent participants within the same cohort may be increased.

A new cohort can be opened when at least participants per cohort are considered DLT evaluable, i.e., if they received 2 doses and either:

- experienced a DLT within the DLT period
- cleared the DLT period without a DLT

The DLT period is 21 days from Day 1/Cycle 1 to Day 7/Cycle 2. If there is a delay in Cycle 2 treatment the DLT period should be adjusted to cover Day 7/Cycle 2 up to a maximum of 35 days, since the maximum dose delay allowed is 14 days.

Once at least participants per cohort are DLT-evaluable, the logistic regression model will be updated with the treatment outcome (i.e., the occurrence of DLT). Thus, a new estimate of the MTD (defined as the dose with the highest probability that the DLT rate is within the target of 20-35% and a relatively low probability <25% that the DLT rate is above 35%) will be derived. In addition, the model will recommend a dose for the new cohort of participants, with the EWOC recommendation being either the new estimate of the MTD or the highest allowable dose based on pre-specified safety constraints (e.g., maximum increments), whichever is lower.

Built in safety constraints are in place to prevent exposing participants to undue risk of toxicity. For instance, in the absence of DLT, the maximum allowable dose-increment will be 200% (i.e., next dose could be as high as 3-fold the previous dose) for dose-levels <700 mg and 100% (i.e. 2-fold) for dose-levels \ge 700 mg. In addition, in case of one event meeting DLT criteria in a dose-level, the maximum allowable dose

increment becomes 100% (i.e. 2-fold); while in the presence of 2 DLTs an increment of 50% is allowed (i.e. 1.5-fold). For further information see Table 1 in Appendix 10.

The dose escalation decision and selection of the dose for the next cohort, guided by the mCRM EWOC recommendation, will also take into account an overall review of safety and available PK and/or PD data as well as any additional data. Subject to clinical judgment, and upon agreement between the Sponsor and the Investigators on the next dose-escalation step, the new cohort can then be opened for enrollment.

The design will continue as described, until one of the pre-defined stopping criteria is satisfied (see Section 4.1.4), or the RDE has been defined, whichever comes first.

4.1.3 **Dose Limiting Toxicities**

For the purpose of this study, a DLT will be defined as any of the following events attributed to RO7121661 (i.e., related to RO7121661) and occurring during the DLT window:

A DLT is defined as a clinically significant AE (classified according to the National Cancer Institute Common Terminology Criteria for Adverse Events [NCI CTCAE] v.5.0, as applicable) or significant laboratory abnormality: 1) occurring during the DLT assessment period of 21 days from the start of the first RO7121661 administration; 2) considered to be related to study treatment RO7121661 by the Investigator and; 3) is not attributed to disease progression or another clearly identifiable cause.

Investigators are encouraged to perform additional tests to determine the underlying etiology and most appropriate attribution.

For the purpose of this study the following AEs are considered DLTs:

- Hematological toxicities:
 - Grade 4 neutropenia (ANC $< 0.5 \times 10^9$ /L) lasting > 5 days.
 - Grade ≥ 3 febrile neutropenia associated with single body temperature > 38.3°C or sustained body temperature ≥ 38°C for > 1 hour, and/or with infection.
 - Grade 4 thrombocytopenia lasting>48 hours.
 - Grade 3 thrombocytopenia associated with bleeding episodes requiring a platelet transfusion.
 - Grade 4 anemia
 - Grade ≥ 3 anemia with hemolysis
- Any non-hematological toxicity of Grade ≥ 3 including:
 - Any Grade 3 immune-mediated AE.
 - Grade 3 hyperbilirubinemia lasting for > 48 hours or Grade 4 hyperbilirubinemia.

- Grade≥3 AST or ALT elevations with hyperbilirubinemia of Grade≥2.
- Grade 4 AST or ALT elevations.
- Grade ≥ 3 nausea, vomiting, or diarrhea despite maximal supportive treatment.
- Grade ≥ 3 non-hematological laboratory abnormality requiring medical treatment/intervention or hospitalization.
- The following Grade ≥ 3 non-hematological toxicity are exceptions for consideration as DLTs:
 - Alopecia (any grade).
 - Grade 3 nausea or vomiting that resolves to Grade ≤ 1 with or without supportive therapy within one week.
 - Grade 3 hypophosphatemia resolved within one week.
 - Grade ≥3 fatigue/asthenia that resolves to Grade ≤2 within one week.
 - Grade 3 anorexia or constipation.
 - IRRs are not considered to be DLTs because, on the basis of experience with mAbs, IRRs are not dose-related events. Hence, IRRs that require removal of participants from the study will be considered as treatment limiting toxicities and not DLTs. Precautions, including pre-medication, will be taken if IRRs of Grade≥2 occur. If described precautions are not sufficient, other options will be discussed between the Sponsor and the Investigator (see Section 8.3.8.1). However, re-occurrence of an IRR event in a participant that precluded the administration of the full dose or the administration of the next scheduled dose of study drug will be considered a DLT. If clinical judgment suggests that an IRR is related to dose (e.g., driven by on-target mediated release of cytokines by immune cells), a Grade 3 or Grade 4 IRR may be considered a DLT.
 - Grade 3 fever (in the absence of any clinically significant source of fever) that resolves to Grade ≤ 2 within 7 days with supportive care.
 - Fever>40°C (i.e., Grade 3) that occurs within 48 hours of RO7121661 infusion and improves to ≤40°C (Grade ≤2) within 48 hours and fully resolves within one week.
 - Grade 3 arthralgia that can be adequately managed with supportive care or that improves/resolves to Grade ≤ 2 within one week.
 - Grade 3 diarrhea, colitis, enteritis that resolves to Grade ≤ 1 within one week with no fever or dehydration.
 - Laboratory values of Grade ≥ 3 that is asymptomatic and that are judged not clinically significant by the Investigator.
 - Grade 3 tumor pain that starts within 24 hours of infusion and improves/resolves to Grade ≤ 2 within one week.
 - Grade 3 tumor flare defined as local pain, irritation, or rash localized at sites of known or suspected tumor.

- Grade 3 neuropathy if the participant began therapy with a Grade 2 neuropathy at baseline.
- Grade 3 hypoxia that starts within 24 hours of infusion and improves/resolves to Grade ≤ 2 within one week.
- In participants with lung lesions, Grade 3 transient dyspnea secondary to localized lung edema that starts within 24 hours of infusion and resolves to Grade 1 or baseline within one week, and transient bronchospasm that resolves within 24 hours.
- In participants with liver lesions, Grade 3 transient increase of bilirubin, transaminases (aspartate aminotransferase [AST]/alanine aminotransferase [ALT]) and/or gamma-glutamyl transferase (GGT) that starts within 24 hours of infusion and recovers to Grade 1 or baseline within one week.

Failure to recover from any RO7121661-related toxicity that results in a dose-delay of the next scheduled administration of more than 14 days is defined as a DLT.

4.1.4 **Stopping Rules Criteria**

Part A Dose Escalation 4.1.4.1

The algorithm of the mCRM with EWOC will propose to stop the dose escalation under the following circumstances:

- The maximum sample size of evaluable participants has been reached **OR**
- Enough information on MTD has been achieved (i.e., at least a minimum of participants enrolled and at least participants have been accrued near the MTD dose - where near is defined as differing from the MTD by at most 15% - and the probability that the MTD dose lies within the target toxicity interval is above 50%)

OR

The maximum dose has been tested and is considered safe (i.e., at least a minimum of participants have been accrued at the maximum dose or near differing from the maximum dose by at most 5% - and it is at least 50% likely that the probability of a DLT for that maximum dose is below 20%).

Due to the exploratory nature of this clinical study, any part of its conduct can be discontinued at any time at the discretion of the Sponsor. This will not constitute a premature termination of the study. The Sponsor will notify the Investigators and Health Authorities if the study is discontinued or the development program is terminated.

4.1.5 **Communication Strategy**

For Part A: Upon completion of all screening evaluations and confirmation that a participant has met all inclusion and exclusion criteria, investigator sites will contact the Sponsor to confirm the dose, participant number and cohort assignment via a Confirmation of Enrollment form (ESF). This will guarantee that the Sponsor is notified

prior to the administration of RO7121661 to any participant. Then sites will need to contact the interactive response technology system (IRT) vendor who will generate confirmation of participant number, dose and cohort assignment. The IRT participant number should be generated prior to first dose.

For Part B: An Interactive Response Technology (IRT) system will be utilized to manage (pre-) screening and enrollment. All pre-screening evaluations must be recorded in the IRT system with a proposed cohort. Roche will review and approve the pre-screened participants for the proposed cohort. After signing informed consent, the screening transaction should be performed in the IRT system and once it is confirmed that participants meet all eligibility criteria the participants should be enrolled in the respective cohort using the IRT system.

A participant Enrollment List must be maintained by the Investigator.

In Part A: After each participant receives RO7121661 the Investigator(s) must confirm to the Sponsor that the participant has been dosed and provide a brief summary of the status of the participant in terms of safety and tolerability to RO7121661. The Investigators and the Sponsor will communicate regularly and on an ad-hoc basis to discuss the occurrence of any safety events including DLTs.

In the event of a DLT, the Investigator will contact the Sponsor immediately (within 1 business day via DLT notification form) to discuss participant status and action taken/to be taken.

In addition, as outlined above, during dose-escalation, after each participant cohort has been completed (i.e., at least participants are DLT evaluable), the Sponsor will organize a teleconference with the Investigators to discuss the safety and tolerability of RO7121661 and to discuss the proposed dose(s) for the next cohort. The dose-escalation decision criteria are outlined in Section 4.1.2.

During these teleconferences, NCI CTCAE Version 5.0 toxicities will be discussed along with the results of any available PK/PD data, in addition to safety laboratory results and any other available data that may assist the dose-escalation decision process. The decision will be based on all relevant available data and not based solely on DLT information, as well as being guided by the mCRM-EWOC recommendation.

Study Investigators and the Sponsor should reach a consensus on the next dose-level which may include dose escalation, de-escalation, or recruitment into the current or particular previously cleared cohorts. Dose-escalation may proceed to the next dose level if the Investigators and the Sponsor are satisfied with the safety profile of the previous participant cohort and agree to move to the next escalated dose level or whether to de-escalate and/or extend recruitment into particular cohorts. The dose discussion will be documented in writing, including the final dose decision whether it is

the mCRM recommended dose, or an intermediate dose, and both the Sponsor and Investigators will approve the Minutes of these meetings to confirm agreement.

In addition to these communications, the Sponsor and Investigators will be in regular contact throughout the study by email/telephone/fax per normal interactions during the conduct of a clinical study and the Sponsor will arrange regular teleconferences and meetings to discuss the study status. The Sponsor will be available 24 hours a day to discuss any medical or study-related issues that may arise during the conduct of this study.

4.2 **JOINT MONITORING COMMITTEE**

In Part B of the study, the Sponsor will in addition form a Joint Monitoring Committee (JMC), with the aim to monitor participants' safety throughout. The JMC will consist of designated Sponsor personnel, including a JMC Chair, clinical scientist, drug safety officer, biostatistician, and independent clinical expert(s) (i.e., expert[s] independent from the Sponsor).

The JMC will conduct regular assessments on an ongoing basis of the incidence and nature of AEs, serious adverse events (SAEs), adverse events of special interest (AESI), frequency of death from all causes, and clinically significant laboratory abnormalities. The JMC will review all safety study data at regular intervals, as defined in the JMC charter.

At the time of each review, the JMC will make one of the following recommendations: the study may continue unchanged, the study is to be stopped, additional analyses are to be performed, enrollment is to be held pending further safety evaluations, or a protocol amendment is recommended. The JMC will report recommendations to the Sponsor.

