- 2. If indicated assessments are performed within 72 hours before dosing days, the assessments do not have to be repeated on the first day of that cycle. If performed on the day of study drug administration they must be done PRIOR to study drug administration. In the event of unexplained abnormal clinically significant laboratory test values, the tests should be repeated immediately and followed up until they have returned to the normal range and/or an adequate explanation of the abnormality is found.
- 3. Triplicate 12-lead ECG recordings (i.e., 3 qualitatively acceptable ECGs without artifacts) must be obtained at screening, at pre-infusion, end of infusion (EOI) and within windows provided at each specified time-point. Patients should be resting and in a supine position for at least 10 minutes prior to each ECG collection. Unscheduled 12-lead ECGs are ONLY REQUIRED as clinically indicated, e.g. there is evidence of QT prolongation on previous ECG assessments. In addition, single ECGs will be recorded in the case of an IRR. Recording must be done prior to PK sampling.
- 4. Complete physical exam (including weight and height at screening only) must be performed during screening, Day 1 of each treatment cycle before study treatment administration, at any unscheduled safety visit, and at study treatment discontinuation, and at the 60-day (Part A) / 90-day (Part B) safety follow-up. At subsequent visits (or as clinically indicated), limited, symptom-directed physical examinations should be performed. Any abnormality identified at baseline should be recorded on the General Medical History and Baseline Conditions eCRF.
- 5. Adverse Events: After initiation of study drug, all AEs and SAEs, regardless of attribution, must be reported until study completion or patient discontinuation, whichever is later. After this period, investigators should report only SAEs that are believed to be related to prior treatment with study drug. Serious adverse events occurring after signature of informed consent but prior to the first infusion of study treatment are reportable according to local regulations. Serious adverse events related to study procedures are reportable following signature of informed consent. For serious adverse events (SAEs) prior to first dose, a corresponding AE page should also be completed.

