- In the event of unexplained abnormal clinically significant laboratory test values, the tests should be repeated immediately and followed up until they have returned to the normal range and/or an adequate explanation of the abnormality is found.
- If such values do not return to normal/baseline within a period of time judged reasonable by the Investigator, the etiology should be identified and the Sponsor notified.

If laboratory values from non-protocol specified laboratory assessments performed at the local laboratory require a change in participant management or are considered clinically significant by the Investigator (e.g., SAE or AE or dose-modification) then, the results must be recorded in the AE CRF.

Results of clinical laboratory testing will be recorded on the eCRF or be received as electronically produced laboratory reports submitted directly from the local or central laboratory.

Additional blood or urine samples may be taken at the discretion of the Investigator if the results of any test fall outside the reference ranges, or clinical symptoms necessitate additional testing to monitor participant safety.

Where the clinical significance of abnormal lab results is considered uncertain, screening lab tests may be repeated before randomization to confirm eligibility.

Based on continuous analysis of the data in this study and other studies, any sample type not considered to be critical for safety may be stopped at any time if the data from the samples collected does not produce useful information.

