However, if the Investigator learns of any SAE (including a death) or other adverse events of concern that are believed to be related to prior treatment with study treatment, at any time after a participant has been discharged from the study, and the Investigator considers the event to be reasonably related to the study treatment or study participation, the Investigator must promptly notify the Sponsor. For the procedure of reporting, see Appendix 2.

8.3.2 Method of Detecting Adverse Events and Serious Adverse Events

Care will be taken not to introduce bias when detecting AEs and/or SAEs. Open-ended and non-leading verbal questioning of the participant is the preferred method to inquire about AE occurrence.

A consistent methodology of non-directive questioning should be adopted for eliciting adverse event information at all participant evaluation time-points.

8.3.3 Follow-Up of Adverse Events and Serious Adverse Events8.3.3.1 Investigator Follow-Up

The Investigator should follow each adverse event until the event has resolved to baseline grade or better, the event is assessed as stable by the Investigator, the event is otherwise explained, the participant is lost to follow-up (Section 7.3), or the participant withdraws consent. Every effort should be made to follow all serious adverse events considered to be related to study treatment or trial-related procedures until a final outcome can be reported.

During the study period, resolution of adverse events (with dates) should be documented on the Adverse Event eCRF and in the participant's medical record to facilitate source data verification. If, after follow-up, return to baseline status or stabilization cannot be established, an explanation should be recorded on the Adverse Event eCRF.

All pregnancies reported during the study should be followed until pregnancy outcome and reported according to the instructions provided in Section 8.3.5.

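### Cycle 1 schedules no hematology or chemistry between Day 5 and Day 15, so laboratory DLTs and other laboratory toxicities can go unseen or undated

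*Combined protocol and SAP*

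**What the plan says.** Section 4.1.3 lists three laboratory DLTs with a duration element: Grade 4 neutropenia beyond 5 days, "Grade 4 thrombocytopenia lasting>48 hours", and "Grade 3 hyperbilirubinemia lasting for > 48 hours or Grade 4 hyperbilirubinemia" (duration applies to the Grade 3 limb only). Section 4.1.2 sets the window: "The DLT period is 21 days from Day 1/Cycle 1 to Day 7/Cycle 2".

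Tables 2 (Part A) and 3 (Part B) place Cycle 1 hematology and chemistry at Day 1 pre-dose, end of infusion and 8 hours, then on Days 2, 3 and 5. The next panels are at Cycle 2 pre-dose and on Cycle 2 Days 2 and 5. The Day 8 and Day 12 rows carry PK and PD samples, but their hematology and chemistry cells are empty. Table 1 shows no Day 8 or Day 12 column.

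Three provisions act outside the fixed schedule:
- Table 1 footnote 2, repeated in Section 8.2.6, says that for unexplained, clinically significant abnormal values "the tests should be repeated immediately and followed up until they have returned to the normal range", or until adequately explained.
- Section 8.2.6 adds: "Additional blood or urine samples may be taken at the discretion of the Investigator", on an out-of-range result or symptoms.
- Section 8.3.3.1 says: "The Investigator should follow each adverse event until the event has resolved to baseline grade or better", or until it is stable or explained.

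None of these ties a retest interval to the 48-hour or 5-day criteria.

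**The concern.** Six of the nine scheduled panels in the 21-day window fall in the first five days, and the stretch from Day 5 to Day 15 has none. A cytopenia or bilirubin rise without symptoms could begin and resolve there without being measured. One first seen on Day 15 would have no known onset, and its duration is counted from onset. The gap also covers laboratory DLTs with no duration element, such as Grade 4 anemia and Grade 4 AST or ALT.

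Under Section 4.1.2 and Table 7, a participant with an unseen event counts as having cleared the DLT period and enters the mCRM-EWOC model as a non-event. That error can only lower the observed DLT count. In Part B, the same blank stretch can lower adverse event incidence, the worst-grade laboratory shifts in Table 9, and the laboratory abnormalities reviewed by the JMC (Section 4.2).

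**Working it through.** **The plan's own figures.** A 14-day cycle plus 7 days gives 21 days, as stated. Adding the 14-day maximum delay gives 35, as stated. Scheduled hours convert by hours/24 + 1, so 96, 168 and 264 h are Days 5, 8 and 12.

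**Length of the gap.** Two windows matter. The Day 5 panel may be taken within ±24 h (Tables 2 and 3). Footnote 2 of Table 1 ("If indicated assessments are performed within 72 hours before dosing days") lets the pre-dose panel be drawn up to 72 h early without a repeat.
- Nominal: 15 − 5 = 10 days.
- Shortest: 12 − 6 = 6 days.
- Longest: 15 − 4 = 11 days.

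Both thresholds (2 and 5 days) fit inside even the shortest gap.

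**Share missed.** Assumptions: onset uniform over the 14 days from Day 1 to Day 15; scheduled tests only; event lengths of 6 days (just over the neutropenia threshold) and 3 days (just over the 48-hour threshold). An event of length L is missed in a gap of length G for G − L days of onset, or for none if L ≥ G. The share missed is the sum of these days divided by 14. If the pre-dose panel is drawn on Day 12 and not repeated, the next panel is on Day 16, which adds a second gap of 4 days.

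| Day 5 panel drawn | Pre-dose panel drawn | Gap(s), days | 6-day event missed | 3-day event missed |
|---|---|---|---|---|
| Day 5 | Day 15 | 10 | 4/14 = 29% | 7/14 = 50% |
| Day 4 | Day 15 | 11 | 5/14 = 36% | 8/14 = 57% |
| Day 5 | Day 12 | 7, then 4 | 1/14 = 7% | (4 + 1)/14 = 36% |
| Day 6 | Day 12 | 6, then 4 | 0% | (3 + 1)/14 = 29% |
| Day 5, with Days 8 and 12 added | Day 15 | 3, 4, 3 | 0% | 1/14 = 7% |

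Among onsets between Day 5 and Day 15 only, at nominal times, the shares missed are 4/10 = 40% (6-day) and 7/10 = 70% (3-day). With the added panels they are 0% and 1/10 = 10%.

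**Proof of duration.** Duration is shown by scheduled draws alone only if two draws inside the episode lie at least 48 h apart (platelets, bilirubin) or 120 h apart (neutrophils). For onsets between Day 5 and Day 15, this happens for 0% of 3-day and 0% of 6-day events, both now and with Days 8 and 12 added. The added panels improve detection; showing duration still depends on repeat tests.

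**A second gap.** From Cycle 2 Day 5 (Day 19) to Cycle 3 pre-dose (Day 29) is another 10 days. It begins inside the 21-day window and is not changed by panels on Days 8 and 12.

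**The case against.** The strongest reply is that duration does not rest on scheduled draws. Once a clinically significant value is seen, the protocol calls for immediate repeats and follow-up, and allows extra samples for symptoms. A reader might infer from the tables that the duration criteria cannot be established at all. The documents do not support that: duration from detection onward can be traced. But a repeat rule needs a first value to trigger it, and cannot find a silent event or date the onset of one first seen on Day 15.

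The miss rates are also sensitive. Event lengths just above the thresholds are near the worst case: at nominal times an episode of 10 days or more is never missed. Permitted early or late draws move the figures a good deal. Adverse events are sought at every contact, including the Day 8 and Day 12 visits, so symptomatic events are less likely to escape. These limits stand, and the ranges above should be read with them.

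Section 4.1.3 also exempts asymptomatic Grade 3 or higher non-hematological laboratory values judged not clinically significant. This weakens the bilirubin example but not the cytopenias.

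Finally, Part A has already led to the 2.1 g dose (Sections 4.3 and 4.4), so the harm to the escalation model is largely past. Table 9 takes the worst grade over all treatment, and no Cycle 1 laboratory analysis is specified. This stands, and it lowers the priority of the point without removing it.

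**Conclusion.** The point holds as a detection and onset problem. For a nominal 10 days (6 to 11 with the permitted windows), no scheduled panel can reveal a silent laboratory toxicity. At nominal times the schedule misses 29% of 6-day and 50% of 3-day events, with ranges of 0-36% and 29-57% across the windows. These figures rest on uniform onset, assumed event lengths and scheduled tests only.

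A reader might infer that the Part A DLT rate, and so the chosen dose, is known to be biased. The documents give no rate for such events. Only the direction of any error (downward) can be stated, not its size or whether it occurred. The practical effect now falls mainly on Part B safety summaries and JMC review, and on any further Part A participants. The change is a cheap improvement to detection, not the repair of a flaw that invalidates the design.

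**What to change.** Mark hematology and blood chemistry at the existing Cycle 1 Day 8 and Day 12 draws in Tables 2 and 3, and carry this into Table 1, for Part B and any further Part A participants. Reconcile the duration criteria in Section 4.1.3 with the repeat-testing rule in Table 1 footnote 2 and Section 8.2.6, so that it is clear how duration and onset are established once a value is seen. Address the stretch after Day 19 at the same time.

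Keep the Day 1 end-of-infusion and 8-hour panels. Moving them to Days 8 and 12 might look cost-free, but Section 4.1.3 has a liver-lesion exception that turns on onset within 24 hours of infusion. Without those panels only the 24 h ± 2 h sample would remain to judge it, and that sample may fall after 24 hours.

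The cost is two local laboratory panels per participant, at venepunctures that already take place.
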